10.6. Appendix 6: Study Tabular Summary

This table is intended for use in posting study information to registries (eg, ClinicalTrials.gov).

Parameter Group	Parameter	Value
Trial information	Trial Title	A Phase 1b, Two-Part, Open-Label, Fixed-Sequence, Safety, Tolerability and Drug-Drug Interaction Study Between Single Dose Erenumab or Galcanezumab and Multiple Dose Ubrogепant in Participants with Migraine
	Clinical Study Sponsor	Allergan Pharmaceuticals International Limited, [name] US Agent: Allergan Sales, LLC, [name]
	Trial Phase Classification	Phase 1b
	Trial Indication	NA
	Trial Indication Type	NA
	Trial Type	Drug-Drug interaction
	Trial Length	45 ± 3 days
	Planned Country of Investigational Sites	United States
	Planned Number of Subjects	40
	FDA-regulated Device Study	No
	FDA-regulated Drug Study	IND #113924
	Pediatric Study	No
Subject information	Diagnosis Group	Participants with migraine for at least 1 year
	Healthy Subject Indicator	No
	Planned Minimum Age of Subjects	18
	Planned Maximum Age of Subjects	50
	Sex of Participants	Both male and female
	Stable Disease Minimum Duration	1 year

Parameter Group	Parameter	Value
Treatments	Investigational Therapy or Treatment	Ubrogapant
	Intervention Type	Drug interaction
	Pharmacological Class of Investigational Therapy	CGRP receptor antagonist
	Dose per Administration	Study Intervention A: Single oral 100-mg dose of ubrogapant tablet on Day 1 Study Intervention B: Single SC injection of 140-mg erenumab on Day 8 Study Intervention C: Two consecutive SC injections of 120-mg galcanezumab on Day 8 Study Intervention D: Repeated once daily oral doses of 100-mg ubrogapant on Days 12, 13, 14, and 15
	Dose Units	mg
	Dosing Frequency	Single and daily
	Route of Administration	Oral (ubrogapant)
	Current Therapy or Treatment	Erenumab and galcanezumab
	Added on to Existing Treatments	No
	Control Type	active
	Comparative Treatment Name	Erenumab or galcanezumab, single dose; subcutaneous administration
Trial design	Study Type	Interventional
	Intervention Model	Parallel
	Planned Number of Arms	2 arms per study part, 2 study parts
	Trial Is Randomized	Yes
	Randomization Quotient	Randomization by study intervention in each part (erenumab in Part 1, galcanezumab in Part 2)
	Trial Blinding Schema	Open-label
	Stratification Factor	None
	Adaptive Design	No
	Study Stop Rules	None

10.7. Appendix 7: Contraceptive Guidance and Collection of Pregnancy Information

Definitions:

Woman of Childbearing Potential (WOCBP)

A woman is considered fertile following menarche and until becoming postmenopausal unless permanently sterile (see below).

Women in the following categories are not considered WOCBP:

1. Premenarchal
2. Premenopausal female with 1 of the following:
 - Documented hysterectomy
 - Documented bilateral salpingectomy
 - Documented bilateral oophorectomy

Note: Supporting documentation from the physician who performed the surgery is needed.
3. Postmenopausal female
 - A postmenopausal state is defined as no menses for 12 months without an alternative medical cause. A high FSH level in the postmenopausal range may be used to confirm a postmenopausal state in women not using hormonal contraception or hormone replacement therapy. However, in the absence of 12 months of amenorrhea, a single FSH measurement is insufficient.

Contraception Guidance:

Male Participants

Nonvasectomized male participants with female partners of childbearing potential are eligible to participate if they agree to the following during the protocol-defined timeframe in Section 5.1 (during the intervention period and for at least 93 days after the last dose of study intervention):

- Agree to use a male condom with spermicide when having penile-vaginal intercourse with a woman of childbearing potential who is not currently pregnant

In addition, nonvasectomized male participants must refrain from donating sperm during the intervention period and for at least 93 days after the last dose of study intervention.

Nonvasectomized male participants with a pregnant or breastfeeding partner must agree to remain abstinent from penile-vaginal intercourse or use a male condom during each episode of penile penetration during intervention period and for at least 93 days after the last dose of study intervention.

Female Participants

Female participants of childbearing potential are eligible to participate if they agree to use an acceptable method of contraception consistently and correctly during the study intervention period and for at least 33 days after the last dose of study intervention.

Acceptable birth control methods include:

- Male or female condom with or without spermicide
- Cap, diaphragm, or sponge with spermicide
- Nonhormonal intrauterine device
- Hormonal contraceptives
- Bilateral tubal ligation
- Bilateral tubal occlusion (eg, Essure[®])

A combination of male condom with either cap, diaphragm, or sponge with spermicide (double barrier methods) are also considered acceptable, birth control methods.

Pregnancy Testing:

- WOCBP should only be included after a confirmed menstrual period and a negative highly sensitive serum pregnancy test at screening and also a negative urine or serum test on Day -1.
- Additional pregnancy testing should be performed during the study intervention period on Day 7.
- Pregnancy testing will be performed whenever a menstrual cycle is missed or when pregnancy is otherwise suspected.

Collection of Pregnancy Information:

Male Participants with Partners Who Become Pregnant

[figure not shown]
- The investigator will attempt to collect pregnancy information on any male participant's female partner who becomes pregnant while the male participant is in this study. This applies only to male participants who receive study intervention.
- After obtaining the necessary signed informed consent from the pregnant female partner directly, the investigator will record pregnancy information on the appropriate form and submit it to the sponsor within 24 hours of learning of the partner's pregnancy. The female partner will also be followed to determine the outcome of the pregnancy. Information on the status of the mother and child will be forwarded to the sponsor. Generally, the follow-up will be no longer than 6 to 8 weeks following the estimated delivery date. Any termination of the pregnancy will be reported regardless of fetal status (presence or absence of anomalies) or indication for the procedure.

[figure not shown]
Female Participants Who Become Pregnant

[figure not shown]
- The investigator will collect pregnancy information on any female participant who becomes pregnant while participating in this study. Information will be recorded on the appropriate form and submitted to the sponsor within 24 hours of learning of a participant's pregnancy. The participant will be followed to determine the outcome of the pregnancy. The investigator will collect follow-up information on the participant and the neonate, and the information will be forwarded to the sponsor. Generally, follow-up will not be required for longer than 6 to 8 weeks beyond the estimated delivery date. Any termination of pregnancy will be reported, regardless of fetal status (presence or absence of anomalies) or indication for the procedure.
- While pregnancy itself is not considered to be an AE or SAE, any pregnancy complication will be reported as an AE or SAE. Abnormal pregnancy outcomes (eg, spontaneous abortion, fetal death, stillbirth, congenital anomalies, ectopic pregnancy) or genetic abnormalities (whether leading to an elective abortion or not) are always considered to be SAEs and will be reported as such. Any poststudy pregnancy-related SAE considered reasonably related to the study intervention by the investigator will be reported to the sponsor as described in Section 8.3.4. While the investigator is not obligated to actively seek this information in former study participants, he or she may learn of an SAE through spontaneous reporting.
- Any female participant who becomes pregnant while participating in the study will discontinue study intervention or be withdrawn from the study.

[figure not shown]

## 2 List of Abbreviations

AUC 0-t	area under the plasma concentration versus time curve, from time 0 to time t, time of last measurable concentration
AUC 0-∞	area under the plasma concentration versus time curve, from time 0 to infinity
BLQ	below limit of quantitation
CDISC	Clinical Data Interchange Standards Consortium
CI	confidence interval
C last	last measurable concentration
CL/F	apparent total body clearance of drug from plasma after extravascular administration
C max	maximum plasma drug concentration
CRF	case report form
CSF	cerebrospinal fluid
CSR	clinical study report
DAP	data analysis plan
ECG	electrocardiogram
EOD	end of dosing
λ z	terminal phase rate constant
ln	natural logarithm
PK	pharmacokinetic
PKS	Phoenix Knowledgebase Server
sFTP	secure file transfer protocol
T ½	apparent terminal-phase half-life
T max	time of maximum plasma drug concentration
V z /F	apparent volume of distribution during the terminal phase after extravascular administration

### **3 Introduction**

The data analyses outlined in this document are to support clinical study 3110-108-002. In this study, measurements will be made for ubrogepant and CGRP concentrations in plasma [REDACTED]. This data analysis plan (DAP) outlines how data analyses of these measurements will be conducted. Additional analysis may be conducted, if necessary. Safety analyses are described separately in the Statistical Analysis Plan.

### **4 Objectives**

The primary objective of this study is to evaluate the effect of single dose erenumab or galcanezumab on the PK of ubrogepant in participants with migraine. The secondary objectives of the study are to evaluate secondary pharmacokinetic (PK) parameters of ubrogepant following administration of ubrogepant and erenumab, or ubrogepant and galcanezumab, and when ubrogepant is administered alone as well as the safety and tolerability profiles when ubrogepant and erenumab or ubrogepant and galcanezumab are administered in combination and when administered alone in participants with a history of 2 or more migraine attacks per month. [REDACTED]

[REDACTED]

[figure not shown]
[REDACTED]

[figure not shown]
### **5 Methods**

#### **5.1 Study Design**

[figure not shown]
This study is a Phase 1b, 2-part, multi-center, open-label, fixed-sequence drug interaction study in 40 male and female participants who have been diagnosed with migraine for at least 1 year and are aged 18 through 50 years. In Part 1, 20 participants will receive a single oral dose of 100 mg ubrogepant alone (Study Intervention A) on Day 1, a single SC injection of 140 mg erenumab alone (Study Intervention B) on Day 8, followed by once daily oral doses of 100 mg ubrogepant on Days 12 through 15 (Study Intervention D) under fasted conditions. Similarly, in Part 2, a separate cohort of 20 participants will receive a single oral dose of 100 mg ubrogepant alone (Study intervention A) on Day 1, 2 consecutive SC injections of 120 mg galcanezumab alone (Study intervention C) on Day 8, followed by once daily oral doses of 100 mg ubrogepant on Days 12 through 15 (Study Intervention D) under fasted conditions.

## 5.2 Analysis Populations

The analysis populations will consist of participants as defined below:

- The safety population includes all participants who receive/take  $\geq 1$  administration of study intervention
- The PK1 population includes all participants who have evaluable plasma PK parameters of ubrogepant for both ubrogepant alone and ubrogepant in combination with erenumab or galcanezumab

- The PK3 population includes all participants who have at least 1 CGRP concentration measurement in plasma

## 5.3 Sample Size Considerations

This is a study to evaluate the safety, tolerability and PK of ubrogepant when co-administered with CGRP MABs. Although the sample size is not based on a statistical calculation, inclusion of 40 participants (20 participants in each part [REDACTED]) is considered reasonable to achieve the objectives of the study.

## 5.4 Software

Pharmacokinetic analysis, summarization of concentration-time data and PK parameter values, and statistical analysis of PK parameter values will be performed using Phoenix® WinNonlin® (Version 8.0 or newer). Tabulations will be exported into Word 2016 (or newer) for formatting. Plotting of concentration-time profiles and scatter graphs (if applicable) will be performed using Phoenix WinNonlin (Version 8.0 or newer), Excel 2016 (or newer) or SigmaPlot 14 (or newer).

## 5.5 Methodology of Measurements

[figure not shown]
### 5.5.1 Pharmacokinetic Methodology

A qualified phlebotomist will collect each participant's blood via an indwelling catheter or venipuncture from either arm into prechilled 4-mL vacutainer tubes containing K2EDTA as an anticoagulant. In Part A and Part B, PK blood samples to determine ubrogepant plasma concentrations will be collected at 0 hour (predose) and 0.25, 0.5, 1, 1.5, 2, 3, 4, 5, 6, 8, 12,

14, and 24 hours postdose on Days 1 and 12. These samples will also be used for the determination of CGRP concentrations.

A total of 52 venous blood samples (26 in Part A and 26 in Part B) per participant will be collected for PK and biomarker analysis. Within 30 minutes from the time of the blood draw, blood samples must be centrifuged at no less than 2500g for 10 minutes at approximately 4°C. After centrifugation, the plasma samples will be harvested and transferred into 2 prechilled, coded polypropylene tube(s). The samples will then be flash-frozen in a dry ice and alcohol bath (with isopropyl alcohol, ethanol, isopropanol, acetone, or methanol) and stored at approximately –20°C or colder.

Total blood volume collected per participant for PK samples is 104 mL (26 blood samples, 4 mL each) in Part A and Part B, respectively.

Plasma concentrations of ubrogepant will be determined using a validated liquid chromatography-tandem mass spectrometry method [redacted]  
[redacted]  
[redacted]

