4.1. Overall Design

This study will be a Phase 1b, 2-part, multi-center, open-label, fixed-sequence drug interaction study in 40 male and female participants who have been diagnosed with migraine for at least 1 year and are aged 18 through 50 years. In Part 1, 20 participants will receive a single oral dose of 100 mg ubrogепant alone (Study Intervention A) on Day 1, a single SC injection of 140 mg erenumab alone (Study Intervention B) on Day 8, followed by once daily oral doses of 100 mg ubrogепant on Days 12 through 15 (Study Intervention D) under fasted conditions. Similarly, in Part 2, a separate cohort of 20 participants will receive a single oral dose of 100 mg ubrogепant alone (Study intervention A) on Day 1, 2 consecutive SC injections of 120 mg galcanezumab alone (Study intervention C) on Day 8, followed by once daily oral doses of 100 mg ubrogепant on Days 12 through 15 (Study Intervention D) under fasted conditions.

If all doses are well tolerated, the duration of participation in the study will be 46 ± 3 days (Day -1 through the safety Follow-up Visit on Day 45), not including the Screening Visit.

- Duration:
 - Screening: Up to 21 days (Day -21 to Day -1)
 - Intervention Period: Up to a total of 17 days (Day -1 to Day 16)
 - Follow-up period: 30 (± 3) days after the last dose

- PK and Biomarker Sampling

In Part 1 and Part 2, PK blood samples for the analysis of ubrogепant and CGRP concentrations will be collected at 0 hour (predose), 0.5, 1, 1.5, 2, 3, 4, 5, 6, 8, 12, 14, and 24 hours postdose on Days 1 and 12.

[REDACTED]

- Safety Measurements

The safety and tolerability profiles when ubrogепant and erenumab or ubrogепant and galcanezumab are co-administered and when each study intervention is administered alone in participants with migraine will be evaluated by clinical assessment of AEs, physical examinations, safety 12-lead ECGs, standard laboratory safety tests (hematology, serum chemistry, and urinalysis), and by measurements of vital signs at specified time points after each study intervention.

- Number of Participants

A total of 40 participants at up to 3 sites in the United States will be enrolled in the study; 20 participants in Part 1 and a separate cohort of 20 participants in Part 2. Part 1 and Part 2 will enroll in parallel. [REDACTED]

██████████. Participants who prematurely discontinue from the study may be replaced at the discretion of the sponsor.

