8.5. Pharmacokinetics

8.5.1. Blood PK Sampling Procedure

Starting on Days 1 and 12, PK blood samples to determine ubrogепant plasma concentrations will be collected at 0 hour (predose) and 0.5, 1, 1.5, 2, 3, 4, 5, 6, 8, 12, 14, and 24 hours postdose. These samples may also be used to determine CGRP concentrations.

PK blood samples should be drawn at the nominal times specified above, relative to the dosing time, and the actual time of the blood draw must be recorded in the source documents and eCRFs. Samples taken more than ± 5 minutes from the nominal time will be noted as protocol deviations, and the reason for deviation must be recorded in the source documents and eCRFs. Predose samples must be drawn within 30 minutes of the dosing time.

Study center staff will record the atomic clock times of all blood draws for each participant and will label Vacutainer and polypropylene tubes with a coded label that corresponds to the

participant number and blood draw time. The study center will supply the coded labels. The study center will be responsible for Vacutainer, polypropylene tubes, and all other supplies.

Any changes in the timing or addition of timepoints for any planned study assessments must be documented and approved by the relevant study team member and then archived in the sponsor and site study files but will not constitute a protocol amendment. The IRB will be informed of any safety issues that require alteration of the safety monitoring scheme or amendment of the ICF.

[figure not shown]
A qualified phlebotomist will collect each participant's blood via an indwelling catheter or venipuncture from either arm into prechilled 4-mL Vacutainer tubes containing K₂EDTA as an anticoagulant ([Appendix 9](#)).

[figure not shown]
Blood Volume Collected per Participant

- Total: approximately 194 mL
- PK and biomarker blood samples: 104 mL (26 blood samples, 4 mL each)
- Screening and end-of-study clinical laboratory analysis: 90 mL

Within 30 minutes from the time of the blood draw, blood samples must be centrifuged at no less than 2500g for 10 minutes at approximately 4°C. After centrifugation, the plasma samples will be harvested and transferred into 2 prechilled, coded polypropylene tubes. The samples will then be flash-frozen in a dry ice and alcohol bath (with isopropyl alcohol, ethanol, isopropanol, or methanol) and stored at approximately -20°C.

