### **5.5.2 Biomarker Methodology**

In Part A and Part B, PK blood samples to determine ubrogepant plasma concentrations will be collected at 0 hour (predose) and 0.25, 0.5, 1, 1.5, 2, 3, 4, 5, 6, 8, 12, 14, and 24 hours postdose on Days 1 and 12. These samples will also be used for the determination of biomarker (CGRP) concentrations. [redacted]  
[redacted]

[redacted]. Plasma and [redacted] of CGRP will be determined using a qualified ELISA assay.

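### Does the SAP's extra 0.25 h sample, with its counts of 26 and 52, leave the primary PK profile undefined?

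*SAP*

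**What the plan says.** The protocol gives one schedule throughout. Section 8.5.1 has samples "collected at 0 hour (predose) and 0.5, 1, 1.5, 2, 3, 4, 5, 6, 8, 12, 14, and 24 hours postdose", and Section 4.1 ties the same times to the two PK days: "0 hour (predose), 0.5, 1, 1.5, 2, 3, 4, 5, 6, 8, 12, 14, and 24 hours postdose on Days 1 and 12". The synopsis (Section 1.1) agrees. Section 8.5.1 also gives the volume, "PK and biomarker blood samples: 104 mL (26 blood samples, 4 mL each"), and a total of about 194 mL once 90 mL of safety blood is added. Section 8 repeats that total.

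The SAP's methods text differs in three ways.

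- **Times.** Section 5.5.1 says samples "will be collected at 0 hour (predose) and 0.25, 0.5, 1, 1.5, 2, 3, 4, 5, 6, 8, 12", then 14 and 24 h. Section 5.5.2 repeats the list: "0.25, 0.5, 1, 1.5, 2, 3, 4, 5, 6, 8, 12, 14, and 24 hours postdose on Days 1 and 12".
- **Counts.** Section 5.5.1 states: "A total of 52 venous blood samples (26 in Part A and 26 in Part B) per participant will be collected". Later in the same section it gives 104 mL per participant, made up of 26 samples of 4 mL.
- **Labels.** Sections 5.5.1 and 5.5.2 say Part A and Part B. SAP Section 5.1 uses Part 1 and Part 2, and states that the parts do not share participants: "Similarly, in Part 2, a separate cohort of 20 participants will receive a single oral dose of 100 mg".

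**The concern.** These samples produce Cmax, AUC0-t and AUC0-∞, the primary endpoints. A reader who counts the SAP's times gets 28, then reads 26, then 52, and may ask which profile will be analysed. The disputed time lies in the absorption phase: protocol Section 2.2 puts peak concentrations at 0.5 to 1.5 h. The extra time appears in two SAP sections, so it is not a slip in a single line, and SAP Section 9 records no changes.

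If sites follow the protocol, the SAP's schedule expects 2 x 40 = 80 samples that nobody draws. If sites do draw them, the protocol understates the blood volume. Data Management, which reconciles assay data against the case report form (SAP Section 5.6), would have three candidate totals to check against.

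**Working it through.** **1. Protocol figures.** Section 8.5.1 lists 0, 0.5, 1, 1.5, 2, 3, 4, 5, 6, 8, 12, 14 and 24 h, which is 13 times.

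- Samples: 13 times x 2 days = 26.
- PK volume: 26 x 4 mL = 104 mL.
- Total: 104 + 90 = 194 mL.

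All three match the stated figures.

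**2. SAP list.** Adding 0.25 h gives 14 times.

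- Samples: 14 x 2 = 28, against the stated 26.
- PK volume: 28 x 4 = 112 mL, against the stated 104 mL.
- Total: 112 + 90 = 202 mL.

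The SAP's figures do not follow from its own list. Reaching 26 from it would mean dropping both predose samples (28 - 2), but the list names the predose sample.

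**3. Where 52 comes from.** 26 + 26 = 52 adds the two parts. The 14-time list would give 28 + 28 = 56. So 52 also rests on the 13-time schedule; the error lies in adding two separate cohorts and calling the sum a per-participant count.

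**4. What each reading does to the analysis.**

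| | 0.25 h not drawn | 0.25 h drawn on both days |
|---|---|---|
| Samples per participant | 26 | 28 |
| PK blood | 104 mL | 112 mL |
| Total blood | 194 mL | 202 mL (+8 mL, 8/194 = 4.1%) |
| PK parameters | from the 13 samples, at actual times | from the 14 samples, at actual times |
| Descriptive tables | empty 0.25 h row | 0.25 h row filled |
| Day 12/Day 1 comparison | same schedule on both days | same schedule on both days |

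The handling rules are in SAP Section 5.6. Parameters use actual times, nominal times serve only descriptive statistics, and postdose samples not collected are missing, with nothing imputed.

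**5. How far one early point can move the parameters.** Assume a predose concentration of zero, rising concentrations with C(0.25) between 0 and C(0.5), and the linear rule on the rising limb.

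- Area from 0 to 0.5 h without the point: 0.5 x C(0.5)/2 = 0.25 x C(0.5).
- Area with the point: 0.125 x C(0.25) + 0.125 x [C(0.25) + C(0.5)] = 0.25 x C(0.25) + 0.125 x C(0.5).
- Difference: 0.25 x C(0.25) - 0.125 x C(0.5), which lies between -0.125 x C(0.5) and +0.125 x C(0.5), in units of hours x concentration.

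Under these assumptions C(0.25) does not exceed C(0.5), so the point cannot set Cmax. That fits the protocol's peak window of 0.5 to 1.5 h. Whatever the small AUC shift is, the same sampling rule applies on Day 12 and Day 1, and the model in SAP Section 7.2 compares the two within participants.

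**The case for a change.** The strongest case for a change is that a specification of primary data should not contradict itself, and that correcting two SAP sections costs almost nothing. The 0.25 h time is written twice. Protocol Section 8.5.1 does let time points be added without a protocol amendment, but only if documented and approved; the SAP cites no such step, and an added sample would not explain the unchanged 26 and 104 mL, or the 52.

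All of that stands as description: the SAP text is wrong somewhere, and the counts cannot all be right. What does not stand is the claim that the primary profile is undetermined. Three places in the protocol give the same 13 times, its volumes reconcile exactly, and Section 8 binds sites to the protocol's schedule. Protocol Section 8.5.1 defines sampling deviations against its own nominal times, so an undrawn 0.25 h sample is not a deviation. A data manager working from the protocol would expect 26 samples per participant, and the SAP's own volume confirms it. If the sample was in fact added, the documented-approval route covers it.

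The ratio could be distorted if 0.25 h were sampled on only one of the two days. Nothing in either document plans that; the SAP's list applies to both. The size of such an effect cannot be computed from the documents.

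**Conclusion.** The discrepancy is confirmed: 28 samples by the SAP's list, against 26 in the protocol and in the SAP's own volume statement, with 52 an arithmetic slip across two cohorts and Part A/Part B a labelling slip. It is clerical. Its practical size is one empty row in descriptive tables (80 sample slots over 40 participants), or, if the sample is drawn, 8 mL more blood per participant against a total given as approximate.

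The primary analysis is unaffected: the parameters, the PK1 population, the mixed model, the 90% confidence intervals and the 80% to 125% limits are the same under either list. This rests on two assumptions: that sites sample to the protocol, or to a documented addition, and that they use the same times on Day 1 and Day 12. The protocol's schedule of activities and its day-by-day supplement cannot be read in the public text, so they could not be checked. The visible sections are enough for an analyst to proceed correctly, and correcting the SAP wording would change no result or conclusion.
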